9.2.2.3. Subgroup Analyses

Subgroup analyses will be conducted for the primary and key secondary endpoints. These will report the descriptive statistics within each subgroup for observed data without imputation and (if feasible) fit the primary MMRM model and report the LSmeans & 95% CIs for each treatment and timepoint. Treatment differences at each timepoint will be reported with the LSmean difference and 95% CI, if estimable.

Subgroups will include:

- Age (>40 years old, <=40 Years old)
- Sex at birth (Male/ Female)
- Race (White/Non-white)
- Ethnicity (Hispanic or latino/ Not Hispanic or latino)

10. SAFETY EVALUATION

10.1. Overview of Safety Analysis Methods

All safety analyses will be completed for the Safety Population. All safety data will be tabulated and listed. No formal statistics or imputation will be performed for the safety analysis. Safety and tolerability will be assessed by:

- Incidence of AEs and SAEs throughout the entire duration of the study
- Incidence of AEs associated with abuse liability using the MADDERS®
- Assessment of physical examination findings
- Changes from baseline (Visit 2) in ECG results
- Changes from baseline (Visit 2) in clinical laboratory test results
- Changes from baseline (Visit 2) in vital signs and weight
- Indications of increased suicidal ideation or behavior as assessed by the C-SSRS
- Changes from baseline (Visit 2) in patient-rated CSFQ-14 in males and in females, assessed separately
- Change from baseline Visit 5 or End of Treatment) in the SOWS at the safety follow-up visit

10.2. Adverse Events

An adverse event (AE) is defined as any untoward medical occurrence in a patient or clinical investigation patient administered an IP that does not necessarily have a causal relationship with this treatment. An AE can therefore be any unfavorable and unintended sign (including an abnormal laboratory finding, for example), symptom, or disease temporally associated with the use of a medicinal product, whether related to the medicinal product, or not.

Pre-existing diseases or conditions will not be considered AEs unless there is an increase in the frequency or severity, or a change in the quality, of the disease or condition. Worsening of a pre-existing condition is considered an AE.

Events that occur in patients treated with placebo, or during treatment free periods of the study, are also considered AEs.

An AE is defined as treatment-emergent if the first onset or worsening is during or after the first administration of IP. AEs (serious and non-serious) that are ongoing at the last study visit should be followed for up to 28 days following the last dose or until one of the above conditions (resolution, etc.) is (are) met. In the case of missing or partial dates, an adverse event will be considered treatment-emergent unless the available data excludes that possibility.

An AE summary table will present totals for the following:

• All treatment-emergent adverse events (TEAEs)

Statistical Analysis Plan: TNX-TI-M201

- TEAEs by severity (mild, moderate, severe)
- TEAEs leading to study drug discontinuation
- TEAEs by relationship (not related, unlikely related, possibly related)
- SAEs

Summaries of incidence rates (frequencies and percentages) of individual AEs by MedDRA SOC and preferred term will be prepared. Such summaries will be displayed for all TEAEs, TEAEs by maximum severity, and TEAEs by strongest relationship to study drug.

Each patient will be counted only once within each summation level (SOC; preferred term). If a patient experiences more than one TEAE within each summation level, the TEAE with the strongest relationship or the maximum severity, as appropriate, will be included in the summaries of relationship and severity.

All AEs will be presented in a listing.

These summaries will include SAEs; additionally, they will be presented separately (see below).

10.3. Deaths, Serious Adverse Events, and Other Significant Adverse Events

Summaries of incidence rates (frequencies and percentages) of individual SAEs by MedDRA SOC and preferred term will be presented. Additionally, SAEs will be listed separately.

TEAEs leading to discontinuation of study drug will be analyzed and presented in a manner identical to the SAEs.

Adverse events potentially related to abuse identified via the Misuse, Abuse, Diversion Drug Event Reporting System (MADDERS®) will be presented in a separate listing.

All deaths will be reported in a listing.

10.4. Clinical Laboratory Evaluation

Laboratory data including Chemistry, Hematology, and urinalyses will be summarized by treatment and visit for the Safety Population. Descriptive summaries of actual values and changes from baseline will be presented by study visit for each clinical laboratory analyte and for each treatment group. 95% confidence intervals will be presented for change from baseline.

Laboratory values will be displayed in the data listings with their corresponding normal ranges, and those values that are outside the normal range will be flagged

Results of urine drug screens and pregnancy tests will be presented in listings.

10.5. Vital Signs, ECGs, Physical Findings, and Other Observations Related to Safety

10.5.1. Vital Signs

Descriptive summaries (mean, SD, median, minimum, and maximum) of actual values and changes from baseline at each assessment time point will be reported for vital signs including weight, body mass index, body temperature, pulse rate, systolic blood pressure and diastolic blood pressure. 95% confidence intervals will be presented for change from baseline. Vital sign values, including abnormal values, will be listed.

10.5.2. ECGs

Descriptive summaries (mean, SD, median, minimum, and maximum) of actual values and changes from baseline at each assessment time point will be reported for each ECG parameter. 95% confidence intervals will be presented for change from baseline.

The ECG interpretation will be performed by the central reader and confirmed by the Investigator, recorded in the CRF as normal, abnormal but not clinically significant, or abnormal and clinically significant. The number and percentage of patients in each category will be reported in shift tables vs the baseline interpretation at each visit.

ECG values, including interpretation, will be listed.

10.5.3. Physical Examinations

Physical examination data will be presented in a data listing

10.5.4. Other Safety Measures

10.5.4.1. Columbia Suicide Severity Rating Scale (C-SSRS)

Based on the C-SSRS results, the overall number of patients with lifetime and/or current suicidal ideation (by item and category), suicidal behavior (by item and category), or self-injurious behavior at the screening and baseline visit will be summarized by visit and treatment group. Additionally, the overall number of patients with any suicidal ideation or behavior (by type and in total) or self-injurious behavior while on-treatment will be provided by treatment group. Patients will only be counted once for on-treatment ideation and on-treatment behavior, at the worst-case response for each item.

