The primary efficacy analysis will use a Mixed Model Repeated Measures (MMRM) approach to estimate mean change from (Visit 2) in the Total MADRS score evaluated at the Week 6 visit in the TNX-601 ER and placebo arms. The model will include all participants in the ITT population, and the dependent variable will be the observed change from Baseline (Visit 2) in total MADRS score at each postdose visit. Covariates in the model will include the fixed categorical effects of treatment, site, visit, and treatment by visit interaction, as well as the continuous fixed covariates of baseline score and baseline score by visit interaction. Missing data will be imputed via multiple imputation (MI), and details regarding the MI approach will be described in the Statistical Analysis Plan (SAP).

The primary analysis will be followed by several sensitivity analyses. The key secondary efficacy outcomes will be measured and compared between treatment groups and will be adjusted for multiplicity using a fixed sequence procedure. Further details on sensitivity and secondary analyses can be found in the SAP, as well as the order of the key secondary endpoints.

Safety Analyses

AEs will be coded using the Medical Dictionary for Regulatory Activities (MedDRA) and will be summarized overall and by preferred term and system organ class. AEs will also be summarized by severity and relationship to study drug. SAEs and AEs leading to discontinuation of study drug will also be summarized. Actual values and changes from Baseline (Visit 2) for clinical laboratory test results, vital signs, ECG parameters, and CSFQ-14 scores will be summarized using descriptive statistics (n, mean, standard deviation (SD), median, minimum, and maximum). The number of patients with Baseline (Visit 2) and treatment-emergent suicidal ideation and/or suicidal behavior, based on the C-SSRS, will be summarized by treatment group.

Interim Analysis

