13.5. Safety Analyses

Safety analyses will be performed using the Safety Population. Safety and tolerability will be assessed by:

- Incidence of AEs and SAEs throughout the entire duration of the study
- Incidence of AEs associated with abuse liability using the MADDERS[®]
- Assessment of physical examination findings
- Changes from baseline (Visit 2) in ECG results
- Changes from baseline (Visit 2) in clinical laboratory test results
- Changes from baseline (Visit 2) in vital signs and weight
- Indications of increased suicidal ideation or behavior as assessed by the C-SSRS
- Changes from baseline (Visit 2) in patient-rated CSFQ-14 in males and in females, assessed separately
- Change from baseline Visit 5 or End of Treatment) in the SOWS at the safety follow-up visit

Adverse events will be coded using MedDRA and will be summarized overall and by preferred term and system organ class. Adverse events will also be summarized by severity and relationship to study drug. Serious AEs and AEs leading to discontinuation of study drug will also be summarized. Actual values and changes from baseline for responses on the CSFQ-14, and actual values and changes from baseline in clinical laboratory test results, ECG parameters, vital signs, and weight will be summarized using descriptive statistics (n, mean, SD, median, minimum, and maximum). AEs associated with abuse liability of the study drug will be evaluated using the MADDERS[®]. Withdrawal symptoms associated with the study drug after the End of Treatment (Visit 5/ET) will be evaluated using the SOWS.

The number of patients with suicidal behaviors, ideations and acts based on the C-SSRS will be tabulated by treatment group and listed. Physical examination data will be presented in data listings.

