3. PROTOCOL SUMMARY

This is a 6-week, randomized, double-blind, placebo-controlled, parallel-group, multicenter study to evaluate the efficacy, safety, and tolerability of TNX-601 ER, 39.4 mg monotherapy, on symptoms of depression in adult patients with MDD in approximately 30 sites in the United States. This study plans to randomize approximately 300 male and female patients aged 18 to 65 years old (inclusive), with current MDD as defined by DSM-5 criteria. During the 6-week double-blind treatment period, patients will receive either TNX-601 ER or placebo in a 1:1 randomization ratio. After the End of Treatment (Visit 5/ET), there will be a 2-week posttreatment safety follow-up period.

The study will be conducted in 4 periods: Screening (Visit 1), Baseline (Visit 2), Treatment (Visits 3-5), and Post Study Follow-up (Visit 6).

Screening (Visit 1)

Patients will be consented and assessed for current MDD as defined by DSM-5 diagnostic criteria, using the Mini International Neuropsychiatric Interview, Version 7.0.2 (MINI 7.0.2). Depression severity will be assessed by MADRS. Eligibility will also depend on medical history, physical and neurological examination, use of concomitant medications, and the results of laboratory tests (eg, pregnancy and drug screen, liver, kidney, and thyroid function, electrocardiogram).

If a patient meets all eligibility requirements but is currently taking a prohibited medication, there will be a Screening Period of up to 35 days for drug tapering and washout. For extenuating circumstances and in cases in which a prospective participant is on fluoxetine, the duration of the Screening Period may be increased to up to 49 days with Medical Monitor approval. Medication-free washout time for prohibited medications will be 4 weeks for antidepressants (except for fluoxetine, which will be 6 weeks) and atypical antipsychotics.

Baseline, Randomization, Start of Treatment (Visit 2)

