To ensure continued eligibility prior to randomization, patients will be assessed for all inclusion/exclusion criteria, including a MADRS total score of \geq 25. Patient must also have a \leq 25% decrease or increase in MADRS score from Screening (Visit 1) to Baseline (Visit 2). Any patients not meeting these randomization criteria will be considered a Screen Failure (SF) and will not continue in the study. Eligible patients will be randomized in a 1:1 ratio to one of two treatment arms (once daily oral TNX-601 ER or placebo). At this visit, study drug will be dispensed, and the first dose will be given to eligible patients.

Double-Blind Treatment Period (Visits 3-5)

The Treatment Period will last for about 42 days. Several investigator- and patient-rated scales and safety assessments (eg, C-SSRS, AEs) will be administered at each visit. At each of the 3 visits, study drug compliance and accountability will be assessed by collecting previously dispensed study drug bottle and counting the remaining tablets.

Statistical Analysis Plan: TNX-TI-M201

All patients who withdraw early from the study will be encouraged to complete an Early Termination (ET) visit as early as possible for safety evaluations. The patients will also be strongly encouraged to come back for the Post Study Follow-up (Visit 6).

[figure not shown]
Post Study Follow-up (Visit 6)

Between discontinuation of study drug and the Post Study Follow-up (Visit 6), potential withdrawal effects will be assessed at home using the SOWS at +1 day, +2 days, +3 days, +6 days, +9 days, and +12 days after the End of Treatment (Visit 5/ET). This includes patients who are early terminated.

Approximately 14 days (+7 days) after discontinuation of study drug, all randomized patients will return to their respective study site for an off-drug, Post Study Follow-up (Visit 6). This visit will include an assessment of prior and concomitant medications, vital signs and weight, pregnancy test, AEs, C-SSRS, and the SOWS.

The overall duration in the study for each patient is expected to be up to 13 weeks.

Figure 1: Study Schema

The study timeline and events schedule are provided in Figure 1.

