8. GENERAL ANAYLSIS AND REPORTING CONSIDERATIONS

Descriptive summaries will be provided where appropriate for each of the primary and secondary variables. In general, tables will summarize data by treatment group and visit.

Continuous, quantitative variable summaries will include the number of patients (N) with non-missing values, mean, standard deviation, median, minimum, and maximum.

[figure not shown]
Categorical, qualitative variable summaries will include the frequency and percentage of patients who are in the particular category. In general, the denominator for the percentage calculation will be based upon the total number of patients in the study population for the treatment group unless otherwise specified.

Unless otherwise specified, baseline values are defined as the last non-missing measurement prior to the first dose of study drug. Change from baseline will be defined as the post-baseline visit value minus the baseline value.

For continuous endpoints where treatment groups are compared via linear models with the difference in LS means, the effect size will be calculated and included as a summary statistic using the difference in LS means and its standard error, transformed to a standard deviation. Study day is defined as assessment date – first dose date +1 for dates after the first dose date and assessment date – first dose date for dates prior to the first dose.

All analyses will be performed using SAS® Software version 9.4 or later.

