8.1.3. Assessment Time Windows

Patients who withdraw/drop out from the study will have the early termination (ET) data collected at their ET visit included in the analysis at the closest visit where a given assessment should be collected per the schedule of assessments (Week 2, 4, 6), using midpoints between

Statistical Analysis Plan: TNX-TI-M201

visits to window the early termination. If this results in two records for a given visit, then the scheduled visit will be used, followed by the record closest to the targeted date. See section 10.5.4.3 for details specific to the SOWs windowing.

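### The SAP's post-baseline C-SSRS count by arm covers an undefined on-treatment period and, read literally, omits the off-drug Visit 6 rating

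*SAP*

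**What the plan says.** The C-SSRS is given at all six visits, using the since-last-visit form from Visit 2 onward (Protocol 11.3.2 and 10.5; schedule in SAP 14.1). SAP section 3 separates the treatment period from the follow-up period and states that "all randomized patients will return to their respective study site for an off-drug, Post Study Follow-up (Visit 6".

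SAP 10.5.4.1 specifies two C-SSRS summaries by arm:

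- Screening and baseline, by visit.
- Post-baseline: patients with any ideation or behavior, or "self-injurious behavior while on-treatment will be provided by treatment group". The counting rule is: "Patients will only be counted once for on-treatment ideation and on-treatment behavior, at the worst-case response for each item".

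The section does not say when on-treatment ends, and it describes no follow-up summary.

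The protocol makes two commitments. Section 13.5 says: "The number of patients with suicidal behaviors, ideations and acts based on the C-SSRS will be tabulated by treatment group and listed". The synopsis says that baseline and "treatment-emergent suicidal ideation and/or suicidal behavior, based on the C-SSRS, will be summarized by treatment group". Neither is confined to time on drug.

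**The concern.** A suicidality rating is scheduled about two weeks after the drug is stopped, yet the analysis plan specifies no comparison of it between arms. The period is not an arbitrary one. The product information appended to the protocol (Appendix 1, English translation, section 4.8) lists post-marketing cases of suicidal ideation and behavior during tianeptine treatment or soon after stopping, with frequency not known. That makes the question plausible but says nothing about its size. Without a specified table, the choice of how to present Visit 6 could be made after unblinding.

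There is a second issue. SAP 10.1 names increased ideation or behavior as the safety measure, and the synopsis asks for treatment-emergent counts. A count of any on-treatment ideation does not compare a patient with his or her own earlier state.

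**Working it through.** The plan gives no figure on this point to reproduce. The check compares texts and counts visits and days.

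**1. Does the specified count reach Visit 6?** The count is limited to on-treatment. The SAP's own label for Visit 6 is off-drug. No ordinary reading of the first includes the second, although the term is undefined.

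**2. Is that narrower than the protocol?** Protocol 13.5 gives a count by arm with no time limit. The synopsis uses treatment-emergent. The only definition of that term in the SAP, for adverse events in 10.2, starts at first dose and has no end date. On the window, the SAP is narrower than both.

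**3. How does the SAP treat other measures taken at Visit 6?** Treatment-emergent adverse events have no cut-off at last dose (10.2), and vital signs are summarized at every assessment (10.5.1). SOWS and the MADDERS survey are also summarized at Visit 6 (10.5.4.3, 10.5.4.4), but they are weak comparators: SOWS is there to measure withdrawal, and the survey is given only at that visit.

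**4. Share of the schedule for a completer** (visit days from the schedule of assessments):

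- Post-baseline ratings are at Visits 3, 4, 5 and 6. Visit 6 share = 1/4 = 25%.
- Nominal time after Day 1: (57 − 43)/(57 − 1) = 14/56 = 25%.
- With visit windows, Visit 5 falls on Day 43 to 45 and Visit 6 on Day 57 to 64. The interval is 57 − 45 = 12 days at the shortest and 64 − 43 = 21 days at the longest.

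**5. Can a plain count show new or worse ideation?** The C-SSRS entry exclusions cover Type 4 or 5 ideation (within 6 months of screening, or at baseline) and suicidal behavior in the past 12 months (Protocol 8.3). Lower ideation types can therefore be present at entry. A patient with the same low-grade ideation before and after first dose is counted in the same way as a patient in whom it is new. For Type 4 or 5 ideation and for behavior the problem largely falls away, because recent history is excluded.

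**6. Would the SAP's visit windowing be a safe basis for the table?** Under SAP 8.1.3, early termination data are "included in the analysis at the closest visit where a given assessment should be collected per the schedule of assessments (Week 2, 4, 6", with midpoints as boundaries, and a scheduled visit takes precedence if two records share a window. Take Visit 3 on Day 15 and early termination on Day 20. The boundary with Week 4 is (15 + 29)/2 = Day 22, so the termination rating maps to Week 2 and gives way to Visit 3. If windowing precedes the worst-case count, that rating is dropped. SAP 10.5.4.1 does not state the order.

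**The case against.** The strongest reply is that nothing in SAP 10.5.4.1 says its summaries are the only ones. SAP 10.1 commits generally to tabulating and listing safety data, and SAP section 8 says: "In general, tables will summarize data by treatment group and visit". This stands in part. The sponsor may well produce a Visit 6 table, and the ratings will be listed. But a general default does not override a specific pooled rule, and a programmer following 10.5.4.1 would not build that table.

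A second reply is that adverse event tables fill the gap. This also stands in part. Protocol 11.3.1 restricts reporting of MDD symptoms to those that, in the patient's view, are significantly worse or more frequent. Significantly worse ideation or new behavior after the last dose should therefore be reported and would enter the by-arm tables. What remains is chiefly unchanged or mildly changed lower-grade ideation, together with the structured rating itself.

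A third reply is that treatment-emergent C-SSRS counts appear only in the synopsis. That is correct. On this question the SAP agrees with Protocol 13.5, and the mismatch begins inside the protocol.

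A reader might infer more than the documents support:

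- *Visit 6 suicidality data are lost.* They are collected and listed.
- *The SAP equates on-treatment with Visits 3 to 5 or early termination.* It gives no definition, and Protocol 10.4.1 allows an early termination visit after a lapse in dosing.
- *The protocol was changed without being declared.* SAP section 12 shows no content in the available text, so this cannot be judged.

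**Conclusion.** The point holds as a gap in the specified comparison by arm, not in data capture. Read literally, the one post-baseline C-SSRS count omits the off-drug rating, which is a quarter of a completer's scheduled post-baseline ratings and of the nominal time after first dose. No effect on counts can be estimated. The secondary point is an inconsistency among the synopsis, Protocol 13.5 and the SAP, and it matters for lower-grade ideation only.

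The conclusion assumes that on-treatment carries its ordinary meaning and that section 12 does not already address the matter. The tables are descriptive and no efficacy inference is touched. The correction should be made before unblinding, but the trial's main conclusions do not depend on it.

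**What to change.** In SAP 10.5.4.1:

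- **Define on-treatment relative to the last dose date.** State how a recall period that straddles the last dose is assigned. Six weeks of daily dosing from Day 1 ends on Day 42 and Visit 5 falls on Day 43 to 45, so a cut-off with no allowance could class a completer's Visit 5 rating as off-drug.
- **Tabulate ideation, behavior and self-injurious behavior by arm** for on-treatment, for off-drug follow-up including Visit 6, and overall after first dose. Use the worst of all ratings in each period, including early termination and unscheduled ratings. Do not apply the one-record-per-visit rule of SAP 8.1.3.
- **Add a count by arm of patients whose worst category after first dose is worse than their pre-dose category.** State the pre-dose recall period from those in Protocol 11.3.2: lifetime or past 6 months for ideation and past year for behavior at screening, and since last visit at baseline. SAP 10.5.4.1 refers to current ideation, which is not one of these periods.

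Reconcile the synopsis with Protocol 13.5 on treatment-emergent counts. If the narrower scope is intended, declare it in SAP section 12.

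The cost is a few extra descriptive tables on data already collected, with no change to study conduct.
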